2.2 Secondary Objective(s) & Hypothesis(es)

Key-Secondary Objectives:

The PLCO_{M2012} model and the NELSON inclusion method will be compared

(ii) secondarily to the primary objective regarding the following hierarchically ordered key-secondary endpoints:

1. Proportion of individuals selected for screening
2. Proportion of lung cancers detected
3. Sensitivity and specificity of the scores in cancer detection

Secondary Objectives:

The main secondary objectives of this trial is to document that:

1. Reporting of the coronary artery calcium score from low dose computed tomography (LDCT) data will lead to an increase in the rate of preventive cardiovascular treatments and reduced cardiovascular mortality.

Additional objectives are to show that:

1. Effective smoking cessation counselling is implemented as part of the screening program (urine cotinine check in quitters).
2. CT derived information on tobacco related lung destruction, such as emphysema, may influence the smoking cessation rate.
3. Structured reporting of clinically relevant non-cardiac incidental findings, e.g., emphysema or lung fibrosis, will lead to early detection and improved management of diseases.
4. Adding the PanCan algorithm/AI to the LungRads1.1 algorithm for nodule management increases the efficiency.
5. Assessment of various blood-based or exhalation-based biomarkers may provide additional translational information in positive LDCT cases with subsequent biopsy, which may have an impact on the effectiveness of the LDCT test.
6. Cost effectiveness analysis on recruiting strategies, risk models used, effectiveness on smoking cessation and cardiovascular mortality is implemented.

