 - c. Percentage of subjects receiving an adequate low-dose CT scan and report according to DRG guidelines (number of diagnostic CTs/number of all CTs)
 - d. Percentage of subjects receiving adequate follow-up procedures
9. **Quality of screening program.**
 - a. CT reading performance (2nd reader vs. CAD vs. AI, positive predictive value)
 - b. Quality of lung nodule management
 - c. Frequency of detection and management of incidental findings from low dose chest CT (emphysema, coronary heart disease, etc.)
 - d. LDCT dose management

10. Smoking cessation

- a. Success of smoking cessation counseling based on number of participants quitting with or without revealing additional health risks (emphysema score, coronary calcium score or both).

11. Blood-based and exhalation-based biomarkers

- a. Evaluation of various blood-based or exhalation-based biomarkers in positive LDCT cases with subsequent biopsy on the positive predictive value of the LDCT test:

Liquid Biopsy:

- Epigenetic Signature Profile from cell free DNA (currently 835 loci), a more specific description is possible after patent approval.

Exhaled Breath Condensates:

- RNA Analysis of the genes TUBA1A and HPRT, followed by analysis for GATA6 Em, GATA6 Ad, NKX2-1 Em, NKX2-Ad.

12. Cost-effectiveness analysis

- a. Cost-effectiveness modeling to investigate the impact of different components of LDCT lung cancer screening on the long-term all-cause mortality and cost-effectiveness: Key components include risk score-based selection criteria, nodule management protocols, threshold values of imaging biomarkers for cardio-vascular diseases and COPD, and inclusion of smoking cessation programs (CHERH).
- b. Comparison of patient recruitment strategies: Cost-effectiveness of register-based mailing campaign vs. GP referrals in terms of recruitment of qualified screening subjects (CHERH).

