- Non-qualifying subjects (who did not meet the NELSON inclusion criteria or PLCO criteria) will be asked to volunteer by contributing long-term outcome data informing of the development of lung cancer or death from lung cancer. In addition NELSON and PLCO non-qualified subjects with a smoking history, who volunteered to participate in the HANSE study, will be contacted via mail after 5 years to inquire if they developed lung cancer in the time between their recruitment and present. Non-responders will be followed by local cancer registries and by phone.

2. **LDCT - 1. Screening round**

- **Lung function test:** All included participants will receive a lung function test prior to undergoing LDCT.
- **Cardiovascular health:** All participants will be questioned whether they receive treatment for any cardiovascular conditions. Blood pressure, heart rate and BMI data (height and weight) will be obtained.
- Assessment of current **COPD treatment medication.**
- **Randomization:** Subjects included in the screening study will be randomized prior to receiving the initial LDCT scan. Randomization will not affect the procedure and the schedule of the cancer screening process but only determine the allocation of the participants of the coronary calcium score and emphysema score to the reporting and the non-reporting group. Randomization ratio of 1:1 and a 2-factorial design ($\frac{1}{4}$ calcium score only; $\frac{1}{4}$ emphysema score only, $\frac{1}{4}$ both; $\frac{1}{4}$ none) will provide equally sized groups of patients in both groups including age (5 year groups) and sex stratification .

Lung LDCT assessment:

- **Standardized and quality-assured image analysis** will be conducted using state-of-the-art artificial intelligence (AI)-based detection and nodule measurement software (Coreline) to support the radiologist. CT assessment of lung nodules will be performed according to LungRADS 1.1 criteria (see Appendix), as well as volume doubling time according to the European position statement on lung cancer screening (14).
- Inspection of **lungs for nodules** will be carried out for all subjects, independent of the assigned groups (reporting or non-reporting).
- An independent 2nd read by an additional radiologist using the same reading software algorithm will be performed.
- Subjects with no nodules or those of LungRADS grades 1, 2, 3, 4a will be scheduled for follow-up scans at intervals according to LungRADS schedule (see Appendix).

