- Prior to obtaining the chest CT, all participants are counselled for smoking cessation and referred to a smoking cessation program, according to the requirements defined by the Joint Statement of the German Radiological Society. Specifically, participation in local certified smoking cessation programs such as “Das Rauchfrei Programm” (<https://www.mhh.de/pneumologie/rauchfrei>) is encouraged. In addition, an information brochure about smoking cessation and available local certified smoking cessation programs and further online information material will be given to each participant.

Biomarker program:

- All patients undergoing tissue sampling according to the LungRADS 1.1. criteria will be invited to participate in the translational biomarker program using a separate informed consent form. For the program, a blood sample for epigenetic profiling will be required, together with an exhalation sample for assessment of specific exhalatory transition markers. The findings of the Biomarker analysis will be correlated to the pathological results of the radiological finding. The exact biomarkers will be determined before the study start and included in the appendix of the protocol.
- Optionally, blood samples will be collected from the high-risk group at the 1st and 2nd screening round visit and stored in the DZL biobank for future research.

Long-term performance and cost-effectiveness:

- The Center for Health Economics Research Hannover (CHERH) develops a comprehensive microsimulation platform for the assessment of long-term performance and cost-effectiveness of nationwide lung cancer screening with LDCT based on the HANSE study data. Main objectives of the modelling study are to investigate the impact of different components of LDCT lung cancer screening on the long-term all-cause mortality and cost-effectiveness. Key components include risk score-based selection criteria, nodule management protocols, threshold values of imaging biomarkers for cardio-vascular diseases and COPD, and inclusion of smoking cessation programs.
- **Model concept:** The stochastic microsimulation model simulates virtual life histories of the HANSE study, which represents a representative sample of the German population in northern Germany. For each individual, it creates different life histories: no LC-screening, LC-screening focussing on lung cancer only, LC-screening including cardiovascular and lung comorbidity assessment, comprehensive LC-screening plus

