- **Assessment of smoking status:** Success of the smoking cessation program will be evaluated using a questionnaire, combined with a urine cotinine check (in quitters).
- **Initiation of COPD treatment:** Assessment of COPD treatment initiation during the study.
- **Consequences of screening:** Questionnaire 'Consequences of Screening' as above.

2. Evaluation

Lung cancer screening:

- The percentage of subjects receiving an adequate low-dose CT scan according to DRG guidelines will be assessed.
- For all included participants, detection rate of lung cancers will be evaluated and categorized according to LungRADS 1.1 categories.
- Detected (proven by histopathology) lung cancers will be categorized whether they were predicted by PLCO or NELSON or both. Statistical analysis will reveal potential advantages of either risk scoring methodology.
- A retrospective analysis will compare this algorithm to the PanCan nodule algorithm vs. AI for management efficiency. Based on the two alternative management algorithms patients are sorted into three management groups: (a) next surveillance scan, (b) early recall scan, or (c) diagnostic evaluation recommended. For one algorithm to be more efficient, the following criteria must both be fulfilled
 - The number of patients without lung cancer sorted in the category (a) is higher AND
 - The number of patients with lung cancer sorted into category (b) or (c) is higher.

Coronary calcium score / cardio-vascular treatment initiation:

- At the 1-year follow-up visit, the rate of initiation of cardiovascular treatment (in particular lipid-lowering) will be determined, together with BMI, and blood pressure data. Data for the calcium score reporting group will be compared to those of the non-reporting group.

Smoking cessation:

- Success of smoking cessation counseling will be based on the number of participants quitting (% quitters) within study period.
- Allocation of the participants to the different experimental groups will allow determining the influence of 'reporting' of prognostic markers (percent emphysema and coronary calcium score) on smoking cessation.

All methods will be performed according to study site SOPs.

CT analysis software (Coreline) specifications:

1. Viewer function

- LCS (Lung Cancer Screening) viewer functions

- Image display with axial, sagittal and coronal images and 3D rendering.
- Virtual slice thickness control display function for MPR (Multi-Planar Reformat) images.

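### The percentage of quitters cannot show that smoking cessation counselling was effective, because every screened participant is counselled and only score reporting is randomised

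*Protocol*

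**What the plan says.** The synopsis and Section 2.2 list, among the things the trial is to show, "Effective smoking cessation counselling is implemented as part of the screening program", with a urine cotinine check in those who quit. Section 6.1.2, under the evaluation of smoking cessation, gives the criterion: "Success of smoking cessation counseling will be based on the number of participants quitting (% quitters) within study period". The endpoint lists in the synopsis and in Sections 4.2 and 5.1.2 use the same label but attach it to the reporting groups: "Success of smoking cessation counseling based on number of participants quitting with or without revealing additional health risks".

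On who is counselled, Section 6.1.2 says that before the chest CT "all participants are counselled for smoking cessation and referred to a smoking cessation program". On what is randomised, the same section says that allocation will "only determine the allocation of the participants of the coronary calcium score and emphysema score to the reporting and the non-reporting group", with a "Randomization ratio of 1:1 and a 2-factorial design": one quarter each for calcium score only, emphysema score only, both, and neither.

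The cost-effectiveness part of Section 6.1.2 builds a microsimulation on the study's data. Its scenarios include no screening, screening for lung cancer only, "LC-screening including cardiovascular and lung comorbidity assessment, comprehensive LC-screening plus" a smoking cessation programme. Experts are to settle the model's structure, and smoking cessation is one of the inputs to be varied in sensitivity analyses.

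**The concern.** A quit rate observed after counselling is an outcome, not an effect. To say that counselling worked, one needs to know how many of the same smokers would have quit without it. The protocol attaches the words effective and success to counselling, but it has no counselled-versus-not comparison and gives no benchmark in place of one.

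Sections 5.2.2 and 5 of the communication material in Section 6.4 aside, the protocol expects its smoking cessation and cost-effectiveness results to guide a national screening programme. A quit rate labelled as the success of counselling could be read there as evidence for the counselling component. If it were also used as the effect of the programme in the cost-effectiveness model, the benefit of adding that programme would be overstated.

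**Working it through.** The protocol states no quit rate, effect size or power for smoking cessation, so there is no figure to reproduce. The check is whether the design can identify an effect of counselling.

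**Inputs from the protocol**
- All screened participants are counselled and referred before the CT (Section 6.1.2).
- Only the reporting of the two scores is randomised (Sections 3.2, 5.2.1 and 6.1.2).
- The low-risk group has no CT. Its later contact asks about lung cancer, and no follow-up of smoking status is stated (Section 4.1.2).
- No external benchmark or success threshold for quitting is given.

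**Step 1: what each group observes.** For baseline current smokers, let b be the quit rate without screening or counselling, s the effect of being screened, c the effect of counselling, and r_C and r_E the effects of reporting the calcium and emphysema scores. Additivity is used only to keep the notation short. The expected one-year quit rates are:

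| Randomised group | Share | Expected quit rate |
|---|---|---|
| Neither score reported | 1/4 | b + s + c |
| Calcium only | 1/4 | b + s + c + r_C |
| Emphysema only | 1/4 | b + s + c + r_E |
| Both | 1/4 | b + s + c + r_C + r_E |

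**Step 2: what can be estimated.** Subtracting rows gives r_C and r_E, because b + s + c cancels. That is the randomised comparison of reporting, and it is valid. The term c appears only inside the sum b + s + c, so no contrast between the groups isolates it.

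**Step 3: the pooled percentage.** Averaged over the four groups, the quit rate is b + s + c + (r_C + r_E)/2. Since 1/4 + 1/4 + 1/4 = 3/4 of participants see at least one score, the pooled figure also contains any effect of reporting.

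**Step 4: bounds.** Take the group with neither score reported and call its quit rate q. If neither screening nor counselling reduces quitting, then c = q − b − s lies anywhere from 0 to q. The standard error of q, √(q(1 − q)/n), shrinks as n grows. The interval from 0 to q does not.

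**Step 5: possible substitutes.** The low-risk group cannot supply b: no smoking outcome is stated for it, and it differs by design in smoking history or risk. A before-and-after comparison does not help either, since baseline current smokers all start as non-quitters. Cotinine testing confirms that a quit is real but not why it happened.

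**Step 6: the model.** If q were entered as the gain from adding the cessation programme, the error would be q − c = b + s. The part s belongs to every screening scenario and the part b to all scenarios. Varying the input shows how far the results depend on it, but does not identify c.

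**The case against.** The strongest reply is that the protocol never plans a causal estimate of counselling. The study is presented mainly as a pilot of a workable programme, access to cessation support is one of the implementation criteria in Section 1.2, and the objective can be read as showing that counselling is delivered and quits are verified. The comparison across groups is already the randomised one: Section 1.2 and the next item in Section 6.1.2 tie it to the influence of reporting. Section 5.2.2 makes all secondary parameters exploratory.

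Much of this stands. It limits the weight of the point, and it means the trial does have a sound cessation comparison, though of reporting. It does not rescue the criterion. If the aim is delivery, the percentage of quitters does not measure delivery. If the aim is effectiveness, that percentage cannot show it. Exploratory status does not change either.

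A reader might go further in three ways that the protocol does not support.
- **That the model inherits an uncontrolled effect.** No section says that the study's quit rate will be the programme effect. The structure is left open. The no-screening scenario is not observed in the screened cohort either, so basing the model on study data cannot mean that every contrast comes from it.
- **That the percentage is taken over all participants, former smokers included.** Section 6.1.2 speaks of participants in the numerator and states no denominator, a detail that may be left to the analysis plan.
- **That any quit rate would count as success.** No threshold is set, and no test of counselling is planned.

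**Conclusion.** The point holds in a limited form. With every screened participant counselled and only score reporting randomised, the percentage of quitters describes quitting under counselling plus screening. It cannot show that counselling was effective, which is what the objective in Section 2.2 and the success criterion in Section 6.1.2 imply.

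The size cannot be given in percentage points, because the protocol contains no quit rates. What can be said is that, if neither screening nor counselling reduces quitting, an observed rate q fits any counselling effect from none to q, whatever the sample size. This rests on the protocol as written: no smoking-status follow-up in an uncounselled group and no stated benchmark.

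The consequence for the microsimulation is conditional. It arises only if the raw quit rate is used as the difference between having and not having the programme. The primary and key secondary endpoints are untouched.

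**What to change.** - **Objective and endpoint (synopsis, Sections 2.2, 4.2, 5.1.2 and 6.1.2).** Replace the language of effective counselling and success of counselling with a descriptive figure: the cotinine-verified one-year quit rate among participants who were current smokers at baseline.
- **Effect claims.** State that conclusions about effects on cessation are limited to the randomised comparisons of calcium and emphysema score reporting, which are already planned.
- **Microsimulation (Section 6.1.2).** Add a sentence saying that the effect of having versus not having the cessation programme will come from controlled external evidence, not from the study's own quit rate. Keep the planned sensitivity analyses around that input.

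No new data, visits or participants are needed: smoking status at entry, the one-year questionnaire and the cotinine check are already in the protocol. The cost is a wording amendment, one decision on a model input, and giving up an effectiveness claim that the design cannot support.

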6.1.3 Quality Control

Monitoring

Offsite Monitoring using plausibility checks during data entry will be performed.

Training of Study Site Personnel

All study personnel will be trained according to the study SOPs prior to the study start.

6.1.4 Storage and Retention

Pseudonymized volunteer data will be stored in a password protected eCRF in a secure environment of the Alcedis Platform. Pseudonymized image data will be stored in a secure password protected cloud environment in Germany. Only the password secured Alcedis TRUST center has access to the clear name and the study pseudonym (Figure 2).

[figure not shown]

Figure 3.

For Image postprocessing and analysis the following **Hybrid system** from Coreline will be used (figure 3):

- Workstations will be installed in each hospital.
- All the DICOM CT images will be stored in the workstation of each hospital.

- Preprocessing, such as lung/lobe segmentation and nodule detection, will be done in each workstation.
- Reading doctors access their images in the workstation through their web browsers.
- Prior exams taken at a different hospital can be accessed (with one-click) in the follow-up mode from DICOM CT images in the CLOUD center.
- All the reading results (reports) are stored in the workstation first.
- All the reading results (reports) will be pseudonymized and uploaded to the secured CLOUD.
- All the DICOM CT images will be uploaded to the CLOUD (Option 1).

6.2 Protection of Human Subjects

This study will be performed in accordance with ethical principles that are consistent with the Declaration of Helsinki, ICH GCPs, GPP and the applicable legislation.

For the study procedures a patient insurance will be obtained. Once the study participant enters the clinical routine, she/he is covered by the insurance of the hospital.

6.2.1 Subject Informed Consent

Before documentation of any data, informed consent (DZL broad consent) is obtained by the patient in writing.

An unconditional prerequisite for a patient participating in the study is his/her written informed consent. Adequate information must therefore be given to the subject by the investigator before informed consent is obtained. A person designated by the investigator may give the information, if permitted by local regulations. A patient information sheet in the local language will be provided for the purpose of obtaining informed consent. In addition to this written information, the investigator or his designate will inform the patient verbally. In doing so, the wording used will be chosen so that the information can be fully and readily understood by laypersons.

The patient information sheet will be revised whenever important new information becomes available that may be relevant to the consent of patients.

The written informed consent of the patient to participate in the clinical study has to be given before any study-related activities are carried out. It must be signed and personally dated by the patient and by the investigator / person designated by the investigator to conduct the informed consent discussion. Patients are also asked to give consent to additional analysis of tumor, blood or urine material. This approval is not a precondition for participation in the study.

Provision of consent will be confirmed in the CRF by the investigator. The signed and dated declaration of informed consent will remain at the investigator's site and must be safely archived by the investigator so that the forms can be retrieved at any time for monitoring, auditing and inspection purposes. A copy of the signed and dated information and consent should be provided to the subject prior to participation.

At any time during or after the HANSE study a volunteer can withdraw from the study without any reason. In this case all collected study data will be deleted.

